Prevention of Postpartum Hemorrhage With Tranexamic Acid
8/9/2018

NCT#03287336

RESEARCH PROTOCOL

TITLE: Prevention of postpartum hemorrhage: pharmacokinetics (PK) and pharmacodynamics (PD) of Tranexamic acid

RESEARCH PLAN

A. Specific Aims

The purpose of this study is to characterize the pharmacokinetics of TXA when given prophylactically at time of delivery. In addition we aim to determine the mechanism of action and pharmacodynamics (PD) of TXA in the peripartum period

B. Background and Significance

Postpartum hemorrhage (PPH) is a significant contributor to maternal morbidity and mortality and is worldwide responsible for approximately *10 maternal deaths every hour*.^{1,2} Prediction for who is at risk for severe hemorrhage is not reliable based on current methods.^{3,4} National organization leaders have called for improvement of recognition and prevention of postpartum hemorrhage.⁵ Aside from uterotonic agents for treatment and/or prevention, few other simple medical interventions exist in the peripartum period.

Tranexamic acid (TXA) is an inexpensive and easy to administer anti-fibrinolytic agent routinely used in cardiac, trauma and orthopedic patients to prevent hemorrhage and reduce mortality. Most of the evidence to support dosing recommendations for clinical studies are based on pharmacokinetic (PK) data from non-pregnant patients.⁴ High dose exposure to TXA among non-pregnant patients is associated with gastrointestinal side effects, seizures and a potential increase in thrombotic risk.⁵⁻⁷ Thus, US obstetricians and anesthesiologists are hesitant to use TXA in the peripartum period especially for prevention of PPH due to uncertainty of an optimal dose and safety profile.⁸

C. Research Design and Methods

The study will seek to enroll 45 3rd trimester pregnant women scheduled for non-emergent cesarean section who are at high risk for hemorrhage towards a target of 30 study subjects to conduct a prospective, open-label, dose finding PK study. We will administer three doses of the drug (5 mg/kg, 10 mg/kg and 15 mg/kg) in an escalating fashion by cohort with the lowest dose first. The drug will be administered intravenously at the time of umbilical cord clamping for a non-emergent cesarean section. A maximum of 1 gram will be administered. TXA serum levels at several time points after delivery will be assayed to see if they reach the target plasma concentration of 10 microg/mL. A PK model will be constructed for determining the optimal TXA dose administered at parturition.

Of note, GW currently has an ongoing randomized clinical trial using tranexamic acid to reduce blood loss in surgery for uterine fibroids (IND# 125089). This study is nearly halfway with recruitment and the research coordinator who is helping with this study will also help with the current proposed study.

Plasma sampling: TXA will be administered by intravenous infusion given over 15 minutes using an infusion pump at the time of umbilical cord clamping. Timing of samples will be relative to the end of the infusion intravenous infusion (start of infusion is t=0) and include before receiving

Group	N	TXA Dose
1	10	5 mg/kg
2	10	10 mg/kg*
3	10	15 mg/kg*

the drug, within 10 minutes, 30-60 minutes, 1.5-3 hours, 4-6 hours, 7-8 hours and 24 hours after the drug load. Each volume of blood draw will be approximately 2-5 mL. The first 10 enrolled patients will receive 5 mg/kg, then the second 10 patients will receive 10 mg/kg and the final set of 10 patients will receive 15 mg/kg. Actual times of plasma sampling will be documented. A second IV will be required for participating in the study. Citrated plasma samples will be centrifuged and supernatant will be stored at -70 degree Celsius for further. Breast milk sampling of no more than 2 cc per time point will occur at time points coinciding with maternal feedings.

*max 1 gram dose

- 1) Subject recruitment and consent. Subject recruitment will take place in the GW MFA routine prenatal clinic among other prenatal patients. In addition, inpatient charting will utilize a screening tool developed for research projects at GW called 'Power Trials' to help screen eligible subjects admitted to L&D. Interested subjects will be consented by either a physician investigator or Research Coordinator as described below. The subjects serum creatine levels will be obtained if indicated at the time of delivery.
- 2) Drug doses will be given in cohort fashion as outlined above with the lowest drug concentration first (5 mg/kg). This will be continued to enroll all participants until the maximum dose of 15 mg/kg (with the absolute max dosage of 1 gram).
- 3) The MFA Investigational Drug Services Pharmacy will provide the drug at the different doses requested. 30 patients in the intervention group will be given a single bolus intravenous injection as described above of TXA at least 10 minutes before.
- 4) Estimated intraoperative blood loss (EBL) will be calculated by measuring the volume in the suction apparatus and weighing the sponges. The weights of dry sponges will be subtracted from the weights of sponges used during the operation. The weight of a sponge found in grams will be translated to ml by using blood density (1.050 g/ml). Thus, estimated intraoperative blood loss will be defined as the blood volume found in the suction apparatus (minus irrigation used) plus the volume calculated for the used sponges. The total perioperative blood loss will be a measure of the intraoperative and postoperative blood loss. In addition, if a patient has an Hb< 7 g/dl and has clinical

symptoms of anemia will be given a blood transfusion. The number of transfusions given will be recorded.

5) The pharmacodynamic testing to be performed includes blood coagulation assays outside the body using patient blood samples. They will assess whole blood clot formation and break down real time and help demonstrate the effects TXA has on these properties. This technology is not routinely used in clinical obstetric care so therefore the information will not be available to be applied to patient care. However, this technology is routinely used for other fields such as cardiac and transplant surgery.

6) Hospital (operative and pathology reports) and clinic (clinical visit notes) reports will be reviewed to compare baseline demographics, preoperative Hb, past surgical history, past medical history and operative time.

D. Study Population:

Inclusion Criteria:

- a. Women who are undergoing medically indicated cesarean section at greater than 34+0 weeks gestation or women undergoing elective cesarean section at 39+0 weeks gestation in accordance with recommendations from the American Congress of Obstetricians and Gynecologists
- b. pregnant women with normal serum creatinine (serum creatinine < 0.9)
- c. Women between the ages of 18 and 50 years old

Exclusion criteria:

- a. Patients younger than 18 or older than 50
- b. women with active thrombotic or thromboembolic disease
- c. Women with a history of arterial or venous thromboembolic event
- d. Women with inherited thrombophilia or preexisting conditions that predisposes them to thromboembolic events (i.e. lupus, antiphospholipid syndrome)
- e. Women with a subarachnoid hemorrhage
- f. Women with acquired defective color vision
- g. history of seizure disorder
- h. known renal dysfunction (serum creatinine >2.0)
- i. multiple gestations (Twin or triplet pregnancies)
- j. Hypersensitivity to Tranexamic acid or anti-fibrinolytic therapy
- k. History of liver dysfunction

Subject Discontinuation Criteria:

- a. Women who experience any serious adverse side effect (including unknown hypersensitivity (hives, shortness of breath, angioedema) or acute thrombosis) while undergoing TXA infusion will be terminated from the study and the infusion of study drug will be discontinued immediately.

The maximum number of patients to be recruited for the study will consist of 30 subjects (10 patients at each dose of the drug specified). This number was chosen as an appropriate sample size for the pilot study.

The Department of Obstetrics and Gynecology at the MFA has seen a dramatic increase in their volume over the past few years. The George Washington University Medical Center (GWUMC) Department of Obstetric Anesthesiology serves a busy Labor and Delivery unit that includes 10 private suites, 4 triage beds, 2 perioperative beds and 2 operating rooms. Obstetrics, nursing and anesthesiology staff are available, in-house 24/7, including resident and attending faculty. It is anticipated that the study coordinator will be available daily during business hours and by an on-call arrangement at other times. Our Labor and Delivery unit has **approximately 3,400 deliveries per year**. The approximate rate of PPH is estimated to be about the national average rate in the US, at 3-5%. Research ROTEM machine and reagents will be provided by ROTEM Inc. and a location for the machine to be stored on Labor and Delivery has been secured. I will use my prior training and experience using ROTEM technology to oversee the PD portion of this project. Frozen samples will be stored in lab space occupied by the Anesthesia department on the 5th floor of Ross Hall.

Study participants will be identified from patients presenting to the GWU Medical Faculty Associates for routine prenatal care. Data including age, pregnancy history such prior cesarean section, uterine fibroids, anemia, prior history of postpartum hemorrhage or blood transfusion will be collected and used to screen for eligible patients.

E. Recruitment and Informed Consent

Recruitment will be performed by one of the prenatal providers who will mention the study to each eligible patient during the patient's routine clinic appointment. The clinician will minimize undue influence by emphasizing the voluntary nature of participation. Furthermore, whenever possible consent procedures will be performed by the research coordinator and not by that patient's physician. A partial HIPAA waiver has been requested in order to review medical records to identify potential participants.

Patients who express interest in the study during scheduled prenatal clinic visits (recruitment) will be contacted directly or by phone by the study's research coordinator. The consenter will ask to meet the patient during her scheduled pre-admission blood work appointment, next scheduled clinic visit, or the day of surgery. Whenever possible, the research coordinator will meet each patient individually to explain the study in greater detail and get each patient's informed consent.

The list of study participants will be maintained in a de-identified coded spreadsheet on the study coordinators password protected computer. The code, linking patient number to MFA medical record number will be separately maintained in a locked file cabinet in the OB/GYN fellow's office.

Informed consent will be obtained by one of the investigators in a non-coercive manner in a private location. All risks, benefits and alternatives to participation will be discussed and the participant will be notified that her decision to or not to participate in the study will in no way influence the quality of care she will receive. The consenter will answer any questions the subject may have. After the study has been explained in detail and they have agreed to participate, signed consent will be obtained and kept on file in a locked cabinet accessible only to research personnel. Subjects will receive a copy of the

signed consent form at the time of consent. Subject recruitment will take place during scheduled preoperative patient visits. Subjects who complete the study will be compensated \$200.00 in the form of a gift card to Target or a Medela breast pump. They will receive the compensation after they have undergone delivery and blood samples are collected.

Subjects will be given the chance to ask questions and to opt out of the research at the recruitment session (during the clinic appointment), the recruitment follow-up (when the research coordinator contacts patients who expressed interest during their clinic appointment) and also at the consent session. Subjects will be reminded of the study on the day of surgery and will have another opportunity to opt out of the study prior to surgery if they wish.

F. Risks and Side Effects:

Potential Risks:

1. *Psychological:* emotional discomfort if a participant assumes a different level of care will be given to those who do or do not participate in this study. However, all efforts will be made to assure patients that participation in this study will not affect the quality of care received. Additionally, patients will undergo informed consent privately in the absence of the clinicians.
2. *Privacy:* There is also a risk of breach of confidentiality. All efforts will be made to ensure that confidentiality is protected. Risk of breach of privacy will be minimized by undertaking both recruitment and consent in the clinic and hospital, at patients' appointments in a private office or exam room. The research coordinator and the clinicians will practice discretion in choosing when to discuss the patient's involvement in the study.

Demographic and study data will be collected and stored in secure password protected digital locations in a de-identified manner. The code linking the study participant number with a patient identifier (MFA medical record number) will be stored in a locked file cabinet in the research coordinators locked office at the MFA. The link between the patient identifiers and the study-related documents will be destroyed 12 months after completion of the study.

3. *Physical:* Tranexamic acid has been studied in a broad range of surgical and obstetrics literature and the risk for venous thrombosis (VTE) is largely theoretical. In the small randomized trials thus far in obstetric literature, there is no increased risk for VTE found. There may be other risks associated with this drug not yet known/published.

Physical risks will be minimized by excluding patients with a prior history suggesting an increased risk for VTE, history of seizure disorder, history of renal ($\text{Cr} > 2.0$) or liver dysfunction, women older than the age of 50, women less than the age of 18. A full listing of exclusions can be found under section.

Potential harm to the neonate should be assessed by asking the mother to self-report any medical diagnosis of the neonate at the 1-2 week follow up call and the 6-week follow up appointment.

We will reassess thromboembolic events for trial participants at the time of discharge from the hospital, 1-2 weeks from C-section by phone call (asking about symptoms such as asymmetrical leg swelling, pain or redness and also shortness of breath) and at 6-week routine postpartum visit.

G. Benefits:

Potential Benefits:

The direct benefit to the patient is that participants in the intervention group may benefit from decreased complications, need for blood transfusions and faster recovery if tranexamic acid does minimize blood loss during cesarean section. Additionally, as many patients with cesarean sections may get repeat operations for delivery during their lifetime, results of this study may inform management of repeat cesarean sections in the future.

The potential indirect benefits of the study are also significant. This research may provide a method to make a common and necessary procedure safer. It may potentially help future studies designed to identify the lowest safest dose for women to use in peripartum period for prevention of postpartum hemorrhage.

H. Costs To Subjects:

1. There is no additional cost to the patient.

I. Conflicts Of Interest:

1. I have a ROTEM Inc Research Machine on loan to conduct the research of my choice. The company has no influence in study design or carrying out the study.

J. Confidentiality:

Each participant will be assigned a study number at the time of consent to participate in the study. All data (demographic, sample labeling, and analytic) will be attached to the study number. No identifiable participant information will be included with these data. De-identified data collection forms will be maintained in secure locked filing cabinets in the research coordinator's office. De-identified data will be entered into spreadsheets on password-protected computers in the research coordinator's office.

The code linking study number to MFA medical record number will be maintained in a single locked file cabinet separate from de-identified data collection sheets by the study research coordinator at the MFA. Access to the participant's medical record will only be available to the study's clinicians and the MFA research coordinator through the MFA's HIPAA compliant, password protected, firewalled electronic medical record (Allscripts).

Following completion of this pilot study and all associated academic publications, presentations, or follow-up grant proposals the de-identified data collection sheets and the code linking participant study number to the MFA medical record number will be destroyed.

K. Subject Compensation:

The subjects who complete the study will be compensated \$200.00 in the form of a gift card to Target or choose to obtain a Medela breast pump valued at \$250. They will receive the compensation after they have undergone delivery and collection of blood samples.

L. Facilities and Equipment

This study will be conducted at George Washington University Hospital Labor and Delivery Operating Room and the GW Medical Faculty Associates OB/Gyn Clinic. All equipment used will be the equipment already planned to be used for the subjects scheduled surgery. No additional surgical equipment necessary. The study drug (IV tranexamic acid) along with associated vials will be purchased.

M. Adverse Event Monitoring and Reporting

Participants will be monitored for adverse events (AEs) by a physical exam performed by the PI or other OB/Gyn physician within 24h hours of administration of the drug. All adverse events will be recorded in real time in an AE log maintained by study staff. AEs will be immediately reviewed and if appropriate, an IND Safety Report will be completed and submitted to the FDA pursuant to CFR Title 21 Part 312 Subpart B §312.32 IND Safety reporting. Additionally, all AEs will be reported to the IRB overseeing the trial in accordance with their requirements.

N. Study Discontinuation

This trial will be stopped and the IRB and FDA immediately notified if any of the following events occur:

- a. Death of one participant
- b. prevalence rate of thromboembolic events in patients that receive TXA exceeds the prevalence background rate of thromboembolic events in this patient population

O. References & Literature Cited

PLEASE REMEMBER TO PAGE NUMBER THE ENTIRE DOCUMENT

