Prevention of Postpartum Hemorrhage With Tranexamic Acid
10/27/2023

NCT#03287336

Statistical Analysis Plan

Study Population

This was a prospective, single-center, open-label, dose-ranging study that recruited thirty pregnant women at The George Washington University from February 2018 to May 2019. Inclusion criteria were normal renal function (serum creatinine < 0.9 mg/dL), and greater than 34 +0 weeks gestation age with planned cesarean delivery. Patients were excluded if they had a thromboembolic history or hypersensitivity to TXA (or any antifibrinolytic therapies). The study protocol was approved by the institutional review board (IRB# 041737), and written consent was obtained from each patient before entering the study.

Dosing and Blood Sampling

Thirty patients were treated sequentially: the first ten patients received 5 mg/kg of TXA, the second ten received 10 mg/kg of TXA, and the last ten received 15 mg/kg of TXA. Total body weight was used to calculate the actual doses, which were capped at 1000 mg. TXA (Cyklokapron®) was given intravenously at the time of umbilical cord clamping and was infused via an infusion pump for approximately 15 minutes (500 mL/hour of 110 mL volume).

Maternal blood samples were collected from the opposite arm of drug administration through peripheral venous catheters or separate venous blood draws. Three samples per patient were taken at each sample time, including pre-drug, 10 minutes, 30-60 minutes, 1.5-3 hours, 4-6 hours, 7-8 hours, and 24 hours post end-of-infusion. One of the three samples for PK analysis was drawn into a tube containing potassium ethylenediaminetetraacetic acid (Becton Dickinson Vacutainer tubes, K2 EDTA 7.2 mg). This sample was further centrifuged at 3000 xg for 15 minutes to obtain platelet-poor plasma. The other two samples for PD analysis were drawn into tubes coated with sodium citrate (Becton Dickinson Vacutainer tubes, Na Citrate 0.109 M, 3.2%). Samples were stored on dry ice until further analysis.

Biomarkers and covariates

TXA concentration determined by ultra-high-performance liquid chromatography-tandem mass spectrometry was used as the PK metric. A modified rotational thromboelastometry (ROTEM) analysis⁹ was used to quantify the anti-fibrinolysis effect of TXA. Maximum lysis (ML), the proportion of clot lysed from the maximum clot (range 0-100%), was chosen as the PD marker to

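### Does the conditional creatinine sentence in the protocol leave the renal eligibility check and the SAP's renal covariates without data?

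*Protocol*

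**What the plan says.** The only protocol instruction for obtaining the test is in section C, Research Design and Methods, item 1: "The subjects serum creatine levels will be obtained if indicated at the time of delivery". No definition of the condition follows.

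Three other places depend on the value:

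- Protocol section D, inclusion criterion b, admits "pregnant women with normal serum creatinine (serum creatinine < 0.9", with no unit, time window or source. The SAP, under Study Population, restates it: "Inclusion criteria were normal renal function (serum creatinine < 0.9 mg/dL".
- Protocol section C fixes when eligibility must be settled: "The drug will be administered intravenously at the time of umbilical cord clamping for a non-emergent cesarean section".
- The SAP, under Biomarkers and covariates, lists serum creatinine (Scr) among the laboratory data from before delivery, says that routine clinical data came from the electronic medical record, and derives creatinine clearance (CrCl) by Cockcroft-Gault. Under Covariate model development it tests both on clearance with a power function, accepting a model that lowers the objective function value (OFV) by more than 3.84.

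Neither document states how many women had a value, or what was done if one had none.

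**The concern.** Taken alone, item 1 seems to make optional the measurement on which criterion b rests. A woman whose creatinine was not thought indicated could then be dosed with her renal eligibility unconfirmed.

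The same value carries both renal covariates, because Cockcroft-Gault uses Scr: a woman without Scr has no CrCl either. Two things would then be at stake in the analysis. OFV differences can be compared only between models fitted to the same observations, so a base model on 30 women and a covariate model on fewer could not be judged by the 3.84 rule. A renal covariate that failed to reach significance would also be harder to interpret if it rested on fewer women than the reader supposes.

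The tubes described in the SAP would not fill such a gap, since they are EDTA and citrate with no serum tube.

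**Working it through.** **1. The plan's own figure.** The critical value of chi-square on 1 degree of freedom at 0.05 is 1.95996² = 3.8415. In reverse, an OFV drop of 3.84 gives P = 0.0500. The threshold is right. It assumes that both models use the same data, which is why completeness of Scr could matter.

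**2. The passages side by side.**

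| Place | What it governs | Is a value needed for each woman? |
|---|---|---|
| Protocol C, item 1 | A draw at the time of delivery | Only if indicated |
| Protocol D, inclusion b | Entry to the study | Yes |
| Protocol E | Medical records reviewed to find candidates; blood work before admission | A possible source of the value |
| SAP, Study Population | The thirty women recruited | Yes, criterion restated |
| SAP, Biomarkers and covariates | Scr from before delivery, from the electronic record | Listed as a data item, no count |
| SAP, Covariate model development | Scr and CrCl on clearance | Yes, for the test to use all 30 |

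Item 1 and criterion b concern different occasions. One sets a condition on an extra draw at delivery; the other sets a condition on entry. Neither cancels the other. A reading that satisfies every row is that eligibility uses a value already on record and that the test is done at delivery when no value is available.

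The routine pathway makes that workable: "The consenter will ask to meet the patient during her scheduled pre-admission blood work appointment, next scheduled clinic visit, or the day of surgery". The contents of that blood work are not listed, so this supports the reading without proving it.

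**3. The count under the plan as written.** Three cohorts of 10 give 3 × 10 = 30 women. If criterion b was applied to each, the number with Scr is 30 of 30. A smaller number requires a departure from criterion b, and no passage suggests one. The bootstrap under SAP Model Evaluation resamples 30 patients. That fits complete data but does not prove it, because the SAP does not say whether a renal covariate stayed in the final model.

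**4. What a missing value would cost.** One woman would be 1/30 = 3.3% of the study and 1/10 = 10% of her cohort. For the covariate test, an illustration needs a correlation *r* between log clearance and log Scr. The documents give none, so 0.4 and 0.5 are assumed. By Fisher's z, two-sided 0.05:

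power = Φ(atanh(*r*) × √(*n* − 3) − 1.96)

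| Women with Scr | *r* = 0.5 | *r* = 0.4 |
|---|---|---|
| 30 | Φ(0.5493 × 5.196 − 1.96) = 81% | Φ(0.4236 × 5.196 − 1.96) = 60% |
| 29 | Φ(0.5493 × 5.099 − 1.96) = 80% | Φ(0.4236 × 5.099 − 1.96) = 58% |
| 24 | Φ(0.5493 × 4.583 − 1.96) = 71% | Φ(0.4236 × 4.583 − 1.96) = 49% |

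One missing value costs 1 to 2 percentage points. A loss of around 10 points needs six women (20%) without a value. These figures show sensitivity only; they are not evidence that anything was lost.

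**5. What a change could achieve.** The SAP reports that the study "recruited thirty pregnant women at The George Washington University from February 2018 to May 2019", and the SAP itself is dated 10/27/2023. Rewriting item 1 cannot affect data collected by then. One extra tube for a woman with nothing on file would have been a small burden (3 tubes × 7 times = 21, rising to 22, or +4.8%), but that option has passed. A SAP sentence asking for the count would alter no model, test or estimate.

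**The case for a change.** The strongest contrary case is that the documents never close the loop. Item 1 is the only instruction to obtain creatinine. The chart review in section C, item 6, names preoperative hemoglobin but not creatinine; the screening data in section D do not name it either, although that list is not presented as complete. Exclusion h covers only known renal dysfunction, so it does not force a test. The SAP relies on routine records and has no rule for a missing covariate. A reader therefore cannot verify from the text that the renal covariate test used all 30 women.

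Most of this stands as description. The condition is undefined, the source of the eligibility value is not stated, and the count is absent. What does not stand is the step from there to a defect. Silence about the source of a value does not make the value optional when an inclusion criterion demands it. The count is a routine entry in a baseline table. If a value were missing, how it was handled would matter more than the count, and an analyst applying a likelihood-ratio rule would in any case fit the competing models to the same observations.

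**Conclusion.** No change to the plan follows. Item 1 is loosely worded and carries a clerical slip (creatine for creatinine), but it is ambiguous rather than contradictory: read as a conditional draw at delivery, it agrees with criterion b and with the SAP's use of pre-delivery values.

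The demonstrated effect on the results is nil. No missing value is shown; if criterion b was followed, 30 of 30 women have Scr and therefore CrCl. This rests on two assumptions: that the criterion was applied as the SAP restates it, and that the electronic record held the value, as the SAP's list of laboratory data implies. Neither can be confirmed from the documents, so the remaining doubt is small but not zero. Giving the number of women with Scr when the results are reported would settle it, and that is ordinary reporting rather than an amendment.

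### Newborn harm is captured only by the mother's report at 1-2 weeks and 6 weeks, with no record check during the birth stay and no stated link to adverse event reporting

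*Protocol*

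**What the plan says.** Newborn harm is addressed in one sentence of protocol section F, Potential Risks, item 3 (Physical): "Potential harm to the neonate should be assessed by asking the mother to self-report any medical diagnosis of the neonate". The timing follows in the same sentence: "neonate at the 1-2 week follow up call and the 6-week follow up appointment".

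The next paragraph of section F gives the mother an earlier contact: "We will reassess thromboembolic events for trial participants at the time of discharge from the hospital". She is then asked about symptoms in the 1-2 week call and reassessed at the routine 6-week visit.

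Four other places bear on the point:

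- Section C, Plasma sampling, on milk: "Breast milk sampling of no more than 2 cc per time point will occur at time points coinciding with maternal feedings".
- Section C, item 6, on records: "Hospital (operative and pathology reports) and clinic (clinical visit notes) reports will be reviewed to compare baseline demographics". The rest of that list covers preoperative hemoglobin, surgical and medical history, and operative time.
- Section M, on monitoring: "Participants will be monitored for adverse events (AEs) by a physical exam performed by the PI or other OB/Gyn physician", within 24 hours of dosing. It continues: "All adverse events will be recorded in real time in an AE log maintained by study staff". AEs are then reviewed, sent to the FDA where appropriate, and reported to the IRB.
- Section N, on stopping the trial: "Death of one participant", and a thromboembolic rate among women given the drug.

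Sections M and N do not mention the newborn. The SAP contains no neonatal outcome and no safety analysis.

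**The concern.** The protocol treats newborn harm as something to assess, and by sampling milk at feedings it recognises that the newborn may be exposed after birth. It also concedes that the drug may carry risks not yet known. Yet the study first asks about the newborn 1-2 weeks after the cesarean. The source is a lay account of diagnoses, and nothing requires that account to be checked.

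At stake is the quality of the newborn safety information. An event during the birth stay may become known late, be described inaccurately, or not reach the study. Once reported, it has no stated path to the people who review AEs and notify the IRB and FDA. If a report of the trial said that no neonatal harm was seen in 30 newborns, a reader could not tell whether nothing happened or nothing was told.

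**Working it through.** The documents give no figure to reproduce, and the point depends on no sample size, power or event rate. The check is a reading of both documents for every assessment, record source and reporting route, with mother and newborn side by side.

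| Stage | Mother | Newborn |
|---|---|---|
| Within 24 hours of dosing | Physical exam (section M) | Nothing stated |
| Hospital discharge | Thromboembolic reassessment (section F) | Nothing stated |
| 1-2 weeks | Symptom call (section F) | Mother asked for diagnoses (section F) |
| 6 weeks | Routine visit (section F) | Mother asked for diagnoses (section F) |
| Record review | Operative, pathology and clinic reports (section C, item 6) | Nothing stated |
| AE log and reporting | Participants monitored; all AEs logged (section M) | Neither included nor excluded |
| Trial stopping events | Death; thromboembolism (section N) | Not mentioned |
| SAP | No safety analysis | No outcome, no safety analysis |

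The newborn column holds two contacts, both by maternal report, and no planned assessment in hospital.

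Now follow a newborn diagnosis made during the birth stay through the plan:

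1. Nobody on the study is scheduled to look for it. The discharge contact exists, but it is limited to the mother's thromboembolic events.
2. The 1-2 week call is the first scheduled opportunity. The delay from event to study is therefore up to 1-2 weeks.
3. If the mother reports it, no step checks it against a record. Section J describes access to the participant's own record in the clinic's electronic system and does not mention a newborn hospital record.
4. If she does not report it then, the 6-week visit is the second and last opportunity.
5. If she reports it at neither contact, it is lost. No step is given for a call or visit that does not take place, and compensation (section K) is due after delivery and blood sampling, so it is not tied to these contacts.
6. Once known, it may be logged, since section M speaks of all AEs. Nothing says that it must be.

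A side note: section C places dosing at cord clamping, while item 3 of the same section describes a bolus at least 10 minutes before something, in a sentence that breaks off. The two must be reconciled, because timing bears on whether exposure before delivery is possible. The present point stands either way.

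**The case against.** The strongest case on the other side is that this is a 30-woman pharmacokinetic pilot, in which open-ended questions at two scheduled contacts are a defensible, low-burden method. Its main arguments, and what stands of each:

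- **Section M covers all AEs.** This stands. A reader might infer that newborn events lie outside the AE system, but that would be read from silence. The supportable statement is that no link is written down.
- **The question covers any diagnosis, so an event in hospital can still surface at the 1-2 week call.** This stands. A reader might infer that a missed 6-week visit loses the event. It does not: the earlier call would also have to fail. The gap concerns timeliness, verification and completeness; capture is not absent altogether.
- **Staff on the unit may hear of events informally.** Possible, but the protocol requires nothing of the kind.
- **The delay hardly affects dose escalation.** This stands. A reader might infer that later cohorts receive higher doses without newborn information that a faster method would supply. The SAP gives 30 women from February 2018 to May 2019, about 15 months: 30/15 = 2 per month, or 10/2 = 5 months per cohort. A two-week lag is about half a month, so on average about 0.5 × 2 = 1 mother per cohort has not yet been asked when the next dose begins (more if enrolment bunched). The protocol also states no safety review between cohorts into which such information would feed.
- **Sample size is the main limit on any safety claim.** This also stands. With complete capture and no events in 30, the one-sided 95% upper limit is 1 − 0.05^(1/30) = 9.5%. A record review does not narrow that limit. It does make a zero count more credible.

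**Conclusion.** The point holds as a modest, inexpensive improvement that should be made. Newborn safety rests on two maternal-report contacts, the first 1-2 weeks after the cesarean. There is no assessment or record check during the birth stay, no verification, and no stated route into the AE log or to the IRB and FDA. The mother's own discharge reassessment shows that the study already has a contact at which this could be done.

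The conclusion rests on the text alone and assumes that the removed consent pages do not set out a newborn follow-up of their own. It affects no pharmacokinetic or pharmacodynamic analysis.

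Two further readings are tempting and not supported. One is that milk in the first days is the main route of exposure: the documents show only that milk is sampled at feedings, and give neither concentrations nor an exposure window. The other is a numerical probability that events would go undetected: the documents give neither a newborn event rate nor a sensitivity of maternal report, so any such figure would be wholly assumed. Nor does the plan announce a claim of neonatal safety. The limitation applies if one is made.

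**What to change.** In section F, have the existing research coordinator review each newborn's hospital record at the mother's discharge, alongside the maternal thromboembolic reassessment. Keep the 1-2 week and 6-week questions. Check any reported diagnosis against the record where one is available, and telephone the mother if the 6-week visit is missed.

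In section M, state that newborn diagnoses, whether found in the record or reported by the mother, are entered in the AE log and follow the same review and IRB and FDA reporting route as maternal events.

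The cost is about 30 record reviews by the existing coordinator and some telephone calls, with no extra visit, sample or patient. Section J would need wording on access to the newborn's record. The consent and privacy authorisation would need it too if it is not already there, which cannot be checked because the consent pages are not available.

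The SAP describes recruitment as complete by May 2019. For women already followed up, the practical remedy is to state in the report that newborn outcomes came from unverified maternal report at two contacts. The wording above would serve any successor study.
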